V2.1	PPD	SAP section 19.1: Additional analysis of patients without the symptom of headache, pruritus and microvascular symptoms (i.e MPN SAF Score =0) and number and percentage of patient with symptom score from 0 to 3, from 4 to 6 and more than 7 are added. Also patients rate with normalized WBCs (WBCs count ≤ 10 x 10 ⁹ /L), Patients rate with normalized platelets (platelets ≤ 400 x 10 ⁹ /L) and Patients rate with normalized haematocrit (haematocrit <45% without phlebotomy) are added. The following tables/figures are added.

Document: PPD

Author: PPD

Version Number:

V2.2

Version Date:

21 March 2018

Template No: CS_TP_BS016 – Revision 3

Reference: CS_WI_BS005

Effective Date: 01May2012

Copyright © 2012 Quintiles Transnational Corp. All rights reserved.

The contents of this document are confidential and proprietary to Quintiles Transnational Corp. Unauthorized use, disclosure or reproduction is strictly prohibited.

		
Tables 14.2.5.1, 14.2.5.2, 14.2.5.3, 14.2.5.4 and figures 14.2.1.18, 14.2.1.19, 14.2.1.20, 14.2.1.21, 14.2.1.22, 14.2.1.23, and 14.2.1.24 are added for Part A.
 
Tables 14.2.6.3, 14.2.6.4, 14.2.6.5, 14.2.6.6 and figures 14.2.1.19, 14.2.1.20, 14.2.1.21, 14.2.1.22, 14.2.1.23, 14.2.1.24 and 14.2.1.25 are added for Part BII.

V2.1	PPD	
Section 20.4: Additional information of 'The number (n) and percentage (%) at baseline, Cycle 3 Day 28 and Cycle 6 Day 28 showed a Spleen Volume reduction \geq 35%' is added.
 
MedDRA dictionary (version 19.0) changed to MedDRA dictionary (version 20.1) and WHO-DRL Drug Dictionary (Version 01MAR2016) changed to WHO-DRL Drug Dictionary (Version 01SEP2017)
 
Section 15.1: '+1' removed from the Per visit" Compliance calculation formula.
 
Added the text 'Also for the last cycle compliance calculation this formula will be used as the last dose of study drug date considering from disposition page.'

V2.2 (Addendum)	PPD	
1. Analysis performed for mathematical application of ELN response criteria (not agreed by the medical site team) and following tables are added.
 
Part A: 14.2.1.1.1, 14.2.1.4.1, 14.2.1.7.1, 14.2.1.8.1, 14.2.1.9.1, 14.2.1.10.1
 
Part B: 14.2.1.1.1, 14.2.1.3.1, 14.2.2.1.1, 14.2.2.2.1, 14.2.2.3.1, 14.2.2.4.1, 14.2.9.1, 14.2.9.3, 14.2.2.7, 14.2.2.8.
 
2. The following tables/Figures are

Document: PPD

Author: PPD

Version Number: V2.2
 Version Date: 21 March 2018

Template No: CS_TP_BS016 – Revision 3
 Effective Date: 01May2012

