3. STUDY DESIGN

3.1. GENERAL DESCRIPTION

This is a two-part, multicentre, open label, non-randomized, phase Ib/II study to assess the safety and tolerability, MTD and preliminary efficacy of Givinostat in patients with JAK2^{V617F} positive PV.

Part A is the dose escalation portion of the Study and, once the MTD has been established, Part B is commenced where the preliminary efficacy of Givinostat in PV patients will be established. Patients are enrolled either in **Part A** or **Part B** and transition from one part to the other is not allowed. Only PV patients from **Part A** assigned to the dose selected for **Part B** (MTD) can be counted towards the efficacy assessment in **Part B**.

Eligible patients for this Study have a confirmed diagnosis of PV according to the revised WHO criteria and the JAK2^{V617F} positivity. Only if the enrolment in **Part A** is slow (i.e. < 5 patients enrolled in 3 months), eligibility for this part of the Study could be expanded to all patients with cMPN.

After providing informed written consent before undertaking any protocol-related procedure, a unique

Document: PPD

Author: PPD

Version Number:

V2.2

Version Date:

21 March 2018

Template No: CS_TP_BS016 – Revision 3

Reference: CS_WI_BS005

Effective Date: 01May2012

Copyright © 2012 Quintiles Transnational Corp. All rights reserved.

The contents of this document are confidential and proprietary to Quintiles Transnational Corp. Unauthorized use, disclosure or reproduction is strictly prohibited.

patient identification code (i.e. patient screening ID which is a combination of his/her site ID, Study part ID and patient screening number, e.g. IT01-A01) is assigned to each patient which will identify the patient within his/her enrolment confirmation by Italfarmaco S.p.A. (Sponsor) or its designee (CRO) and can never be reused in case of screening failure. After the enrolment confirmation and the assignation of the dose level before the first drug intake, a unique patient identification code (i.e. patient ID which is a combination of patient screening number ID and dose level ID, e.g. IT01-A01-DL1) is assigned to each patient which will identify the patient throughout his/her participation in the Study and can never be reused in case of premature drop-out.

Study therapy is administered in 28 day cycles. In fact, the “cycle” is defined as 4 weeks of treatment.

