3.2.1. DEFINITION OF DOSE LIMITING TOXICITY (DLT)

DLT is defined as the following drug-related toxicity:

- Grade 4 haematological toxicities, or
- Grade 3 febrile neutropenia, or
- Grade ≥ 3 non-haematological toxicities with exception of:
 - a) Grade 3 diarrhoea without adequate supportive care lasting less than 3 days, and
 - b) Grade 3 nausea or vomiting without adequate supportive care lasting less than 3 days, or
- Any drug-related SAE, or
- Any toxicity that is clearly not related to disease progression or intercurrent illness requiring interruption of dosing for more than 3 days during the first cycle.

The severity of the above mentioned events is graded according to NCI Common Terminology Criteria for Adverse Events (CTCAE v. 4.03, 14th June 2010).

Only DLTs experienced during the first cycle of treatment are considered for dose escalation decisions. DLTs included all Adverse Events that are clearly not related to disease progression or intercurrent illnesses.

Patients who do not experience a DLT and miss more than 10% of the doses in Cycle 1 of Part A should be replaced (see [paragraph 4.6.4](#) of the Study protocol version 3.0).

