5.4. MAXIMUM TOLERATED DOSE ANALYSIS SET (MTD)

The MTD analysis set will include all patients who experienced DLTs in Cycle 1 of **Part A**, or who received at least 90% of the doses of study medication in Cycle 1 of **Part A**. The data regarding the Cycle 1 of **Part A** will be used to determine MTD from this analysis set.

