15. STUDY MEDICATION COMPLIANCE

The Investigator recorded in the electronic CRF the assigned dose of Givinostat and any dose reduction (*if applicable*) to allow the evaluation of compliance to treatment. At each visit, patients brought back to the Study site all drug bottles previously received (i.e. used, partially used and unused) and receive a new Study drug supply. The number of residual capsules in the dispensed bottles were counted by the Investigator and reported in the electronic CRF.

Compliance with Givinostat treatment will be calculated based on the Study drug accountability documented by the site staff and monitored by Italfarmaco S.p.A. or its designee (i.e. capsule counts).

A patient will be considered sufficiently compliant with Givinostat treatment if he/she has taken at least 80% of the prescribed dose over the total duration of Study drug dosing. In addition, patients who didn't experience a DLT and missed more than 10% of the doses in Cycle 1 of **Part A** will be considered not sufficiently compliant.

Treatment compliance to Study drug will be presented for the SAF analysis set, ITT analysis set, PP analysis set, MTD analysis set and PK analysis set, during all six Cycles of treatment (i.e. from C1D1 to C6D28). Treatment compliance will be calculated for C1D1 – C1D28 in **Part A**, and C1D1 – C6D28 in **Parts A and B** (both Stages).

Treatment compliance per interval is defined as the number of capsules that were actually taken within a given interval relative to the number of capsules that should have been taken by the patient for the duration of actual treatment exposure for that interval.

Summary statistics for the Actual Total Dose delivered (mg), Givinostat Dose Intensity (mg/day) will be presented.

Summaries showing Givinostat dose modification during the Study will be presented by treatment group.

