15.1. DERIVATIONS

In general, the percentage compliance (%), assessed by capsule count, will be calculated as follows:

Document: PPD

Author: PPD

Version Number:

V2.2

Version Date:

21 March 2018

Template No: CS_TP_BS016 – Revision 3

Reference: CS_WI_BS005

Effective Date: 01May2012

Copyright © 2012 Quintiles Transnational Corp. All rights reserved.

The contents of this document are confidential and proprietary to Quintiles Transnational Corp. Unauthorized use, disclosure or reproduction is strictly prohibited.

- “Per visit” Compliance to study medication will be calculated as follows:

$$\frac{\{([N \text{ of Capsules dispensed at Visit } (n)] - [N \text{ of Capsules returned at Visit } (n+1)])\}}{[[\text{Date of Visit } (n+1)] - [\text{Date of Visit } (n)]] \times \text{Number of capsules prescribed by day}} \times 100$$

- Overall Compliance to study medication will be calculated as follows:

$$\frac{\{([N \text{ of Capsules dispensed at Cycle 1}] - [N \text{ of Capsules returned at Cycle 2}]) + \dots + ([N \text{ of Capsules dispensed at Cycle}(n-1)] - [N \text{ of Capsules returned at Cycle}(n)])\}}{[[\text{Date of Cycle}(n)] - [\text{Date of Dispensing at Cycle 1}]+1] \times \text{Number of capsules prescribed by day}} \times 100$$

Also for the last cycle compliance calculation this formula will be used as the last dose of study drug date considering from disposition page.

For patients who permanently stop the study medication, the “Date of visit (n)” will be replaced by the date of study withdrawal.

A patient will be considered sufficiently compliant with Givinostat treatment if he/she has taken at least 80% of the prescribed dose over the total duration of study drug dosing.

The calculated percentage compliance per interval will be categorized as:

A) **Part A** – Cycle 1:

- Too Low: ≤ 90% compliance.
- Adequate: > 90% to ≤ 100% compliance.
- Too High: > 100% compliance.

B) **Part A** (all Cycles) and **Part B:**

- Too Low: < 80% compliance.
- Adequate: ≥ 80% to ≤ 100% compliance.
- Too High: > 100% compliance.

Document: PPD

Author: PPD

Version Number:

V2.2

Version Date:

21 March 2018

Template No: CS_TP_BS016 – Revision 3

Reference: CS_WI_BS005

Effective Date: 01May2012

Copyright © 2012 Quintiles Transnational Corp. All rights reserved.

The contents of this document are confidential and proprietary to Quintiles Transnational Corp. Unauthorized use, disclosure or reproduction is strictly prohibited.

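### The per-visit compliance denominator runs one day short of the overall and exposure conventions, so the Part A Cycle 1 percentage and category depend on an unstated Day 28 counting rule

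*SAP*

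**What the plan says.** Section 3.1 of the SAP fixes the cycle length: "Study therapy is administered in 28 day cycles". Section 15 asks for a Cycle 1 figure in Part A ("Treatment compliance will be calculated for C1D1 – C1D28 in" Part A) and defines compliance per interval as capsules taken relative to the "number of capsules that should have been taken by the patient for the duration of actual treatment exposure for that interval".

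Section 15.1 gives two formulas. The per-visit denominator is the date of the next visit minus the date of the current visit, times capsules per day. The overall denominator is the date of the last cycle visit minus the first dispensing date, plus one, times capsules per day. The change log records that V2.1 took the plus one out of the per-visit formula. Section 14.1 derives exposure as last dose date minus first dose date, plus one.

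For Part A Cycle 1 the per-interval categories are Too Low at 90% or below, "Adequate: > 90% to ≤ 100% compliance", and Too High for anything above 100%.

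Two other rules use a similar threshold. Section 5.4 admits to the MTD set patients with a DLT "or who received at least 90% of the doses of study medication in Cycle 1 of" Part A. Section 3.2.1 says: "Patients who do not experience a DLT and miss more than 10% of the doses in Cycle 1 of Part A should be replaced".

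**The concern.** Dropping the plus one is right for an interval from one Day 28 visit to the next, which already spans 28 days. The first interval is different: it starts on Day 1, so the date difference is 27 although the cycle covers 28 dosing days. Under the exposure convention of 14.1, which the definition in Section 15 points towards, it should count as 28.

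The Cycle 1 bands have hard edges at 90% and 100%, so one day in 28 is enough to change a category at either end. Part A dose levels hold three to six patients, so a single wrong label is visible in the table. It could show a fully adherent patient as taking too much, or show as Adequate a patient who missed more than the 10% that Section 15 itself calls not sufficiently compliant.

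**Working it through.** **Inputs.** Cycle length 28 days (3.1). Part A Cycle 1 visits on Days 1, 2, 3, 4, 8, 10, 15, 22 and 28 (Table 3). Twice-daily dosing at DL1 and DL0, three capsules a day at DL6 (Table 1.1). Formulas and bands from 15.1. Visits are assumed to fall on their nominal days.

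**Denominators.**
- C1D1 to C1D28 by the per-visit formula: 28 − 1 = 27 days. Visit by visit: 1+1+1+4+2+5+7+6 = 27, the same.
- C1D1 to C1D28 by the 14.1 convention: 28 − 1 + 1 = 28 days.
- Six cycles, per-visit: 27 + 28 + 28 + 28 + 28 + 28 = 167 days.
- Six cycles, overall formula: 168 − 1 + 1 = 168 days.

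**Cycle 1 on twice-daily dosing.** The per-visit divisor is 27 × 2 = 54 doses. The numerator depends on how many Day 28 doses are counted against the Cycle 1 supply.

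| Day 28 doses counted in Cycle 1 | Doses due | 0 missed | 6 missed | 7 missed | 8 missed |
|---|---|---|---|---|---|
| Both | 56 | 56/54 = 103.7%, Too High | 50/54 = 92.6%, Adequate (10.7% missed) | 49/54 = 90.7%, Adequate (12.5% missed) | 48/54 = 88.9%, Too Low |
| Morning only | 55 | 55/54 = 101.9%, Too High | 49/54 = 90.7%, Adequate (10.9% missed) | 48/54 = 88.9%, Too Low | 47/54 = 87.0%, Too Low |
| None | 54 | 54/54 = 100.0%, Adequate | 48/54 = 88.9%, Too Low (11.1% missed) | 47/54 = 87.0%, Too Low | 46/54 = 85.2%, Too Low |

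In the first two rows the label is wrong at full adherence and at six missed; in the first row it is also wrong at seven. In the third row every label is right.

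**Width of the wrong Adequate band.** With both Day 28 doses counted, a reading of 90% corresponds to true adherence of 0.90 × 27/28 = 86.8%. The band therefore runs from just over 10% to about 13.2% of doses missed. Three capsules a day (84 due, divisor 81) gives the same picture: 9 to 11 missed, or 10.7% to 13.1%.

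**Where the day goes if no Day 28 dose belongs to Cycle 1.** Each interval then runs from one visit day up to the day before the next. If the last interval uses the per-visit formula and ends at the last-dose date on C6D28, it holds the doses of Days 140 to 168. That is 29 days of doses over a 28-day difference: 29/28 = 103.6%, or 28.5/28 = 101.8% if only the morning dose is taken on the final day.

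**Effect of a 28-day divisor in Cycle 1 (56 doses).**
- Both Day 28 doses counted: 56/56 = 100.0%; 6 missed, 50/56 = 89.3%; 7 missed, 49/56 = 87.5%. All labels are right.
- Morning only: 5 of 55 missed (9.1%) gives 50/56 = 89.3%, Too Low, which is wrong.
- None: 4 of 54 missed (7.4%) gives 50/56 = 89.3%, Too Low, which is wrong.

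**The case against.** The best defence is that 27 days may be correct for Cycle 1. Section 15 says all bottles come back at each visit and a new supply is handed out. Section 3.4.1 says the morning dose on PK days is given in the clinic, and the abbreviations list treats Day 28 as a pre-dose sampling day. If the in-clinic dose and the evening dose both come from the new supply, no Day 28 dose is counted in Cycle 1 and the labels are right. This stands, and it is why the misclassification is conditional. It also means that adding a day to Cycle 1 without settling the question could create new errors. It does not reconcile the 167 and 168 days.

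A second defence is that 15.1 does not clearly say which formula feeds the Part A Cycle 1 category. Cycle 1 spans several visits, and the overall formula, which has the plus one, is the one that sums over several supplies. This also stands: the SAP is unclear, not demonstrably wrong, on that choice. The sentence about the last cycle is similarly loose about which formula it means.

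A reader might go further and infer that MTD-set membership or patient replacement was distorted. The SAP does not support that. Sections 5.4 and 3.2.1 define both directly on doses received or missed, and neither refers to the 15.1 percentage. Section 3.7 also places the MTD decision in July 2015, before this SAP version of March 2018.

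**Conclusion.** The inconsistency is real and rests on date arithmetic alone: the per-visit denominators total one day less than the overall formula and the exposure convention. If every interval, including the last to the last-dose date, uses the per-visit formula, a fully adherent patient must exceed 100% in at least one interval, because 168 days of doses (167.5 if only the morning dose is taken on the final day) are spread over 167 days of denominators.

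The wrong Cycle 1 labels follow only if the per-visit formula feeds that category and at least one Day 28 dose is counted against the Cycle 1 supply. Full adherence then reads 1.9 to 3.7 percentage points too high, and six missed doses read as Adequate. It is not the case that anyone missing more than 10% would pass: at eight of 56 missed the label is correctly Too Low. These figures assume visits on nominal days. What is exposed is a descriptive compliance table; no efficacy result is affected, and no effect on the MTD set is shown. The point is still worth correcting, because a stated rule can give a wrong category in very small cohorts.

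**What to change.** In Section 15.1:
- State which supply the doses of a visit day (Day 28) are counted against, including how the day is treated if its morning and evening doses come from different supplies.
- State which formula gives the Part A Cycle 1 figure and which gives the last-cycle figure.
- Add the extra day to exactly one interval so that the per-visit and overall denominators agree: C1D1 to C1D28 if Day 28 doses belong to Cycle 1, otherwise the last interval, ending at the last-dose date. Leave the other intervals as they are.
- State that the Cycle 1 category and membership of the MTD set both use doses taken over doses due in Cycle 1.

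The denominator change itself costs one sentence and one programming condition; the other items are short clarifications of wording. No new data are needed beyond the capsule counts and dates already collected.

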16. EFFICACY AND SAFETY VARIABLES

16.1. DEFINITION OF END OF THE STUDY

The end of the Study (last patient last visit) will occur after all patients in whole Study (**Part B**) have completed their last assessment as per Study protocol. Note that the analysis of the biological samples could be performed after the end of Study due to scientific (i.e. after evaluation of preliminary results and data exploration, some additional analyses could be performed to identify and quantify other molecular parameters of interest in term of improving of the knowledge of cMPN and the activity of the drug in these disorders) or technical reason.

In any case, after the completion of the analysis all data should be formally reported in a Clinical Study Report and/or in a specific technical report.

16.2. EFFICACY ASSESSMENT

Timing information are summarised in the Study flow-chart ([Appendix A](#) of the Study protocol) and detailed in the [paragraph 4.5.4](#) of the Study protocol.

Document: PPD

Author: PPD

Version Number:

V2.2

Version Date:

21 March 2018

Template No: CS_TP_BS016 – Revision 3

Reference: CS_WI_BS005

Effective Date: 01May2012

Copyright © 2012 Quintiles Transnational Corp. All rights reserved.

The contents of this document are confidential and proprietary to Quintiles Transnational Corp. Unauthorized use, disclosure or reproduction is strictly prohibited.

16.3. CRITERIA FOR ASSESSING CLINICO-HAEMATOLOGICAL IMPROVEMENT

Disease response will be evaluated according to the following clinico-haematological ELN criteria [1] after 3 and 6 cycles (i.e. at weeks 12 and 24, respectively) of treatment with Givinostat both in **Part A** (exploratory endpoints) and in **Part B** (primary and secondary endpoints, respectively).

- **Complete response:**
 1. HCT < 45% without phlebotomy, and
 2. Platelets $\leq 400 \times 10^9/L$, and
 3. WBC $\leq 10 \times 10^9/L$, and
 4. Normal spleen size, and
 5. No disease-related systemic symptoms (i.e. pruritus, headache, microvascular disturbances).

- **Partial response:**

Patients who do not fulfil the criteria for complete response and

 1. HCT < 45% without phlebotomy, or
 2. Response in 3 or more of the other criteria.

- **No response:** any response that does not satisfy partial response.

Only in case the enrolment in **Part A** is slow (i.e. < **5 patients enrolled in 3 months**) and the eligibility for this part of the study may be expanded to all patients with cMPN, disease response for this part of the study can be evaluated according to the clinico-haematological ELN and EUMNET criteria [7] after 3 and 6 cycles of treatment with Givinostat, in ET and MF patients, respectively.

For ET (from the clinico-haematological ELN response criteria):

Document: PPD

Author: PPD

Version Number:

V2.2

Version Date:

21 March 2018

Template No: CS_TP_BS016 – Revision 3

Reference: CS_WI_BS005

Effective Date: 01May2012

Copyright © 2012 Quintiles Transnational Corp. All rights reserved.

The contents of this document are confidential and proprietary to Quintiles Transnational Corp. Unauthorized use, disclosure or reproduction is strictly prohibited.

- **Complete response:**
 1. Platelets $\leq 400 \times 10^9/L$, **and**
 2. No disease related systemic symptoms (i.e. pruritus, headache, microvascular disturbances), **and**
 3. Normal spleen size, **and**
 4. WBC $\leq 10 \times 10^9/L$.

- **Partial response:**

Patients who do not fulfil the criteria for complete response and

 1. Platelet count $< 600 \times 10^9/L$, **or**
 2. Platelet count decrease $> 50\%$ from baseline.

- **No response:** any response that does not satisfy partial response.

Both for PV and ET patients, all phlebotomies performed in the first 3 weeks of treatment are **not** counted to assess the clinico-haematological response.

For MF (from EUMNET response criteria)

- **Complete response:** complete response in anemia, splenomegaly, constitutional symptoms, platelet and leukocyte count.
 1. Complete response in anaemia: Haemoglobin ≥ 12 g/dL for transfusion-independent patients or ≥ 11 g/dL for transfusion-dependent patients (applicable only for patients with baseline haemoglobin level of < 10 g/dL);
 2. Complete response in splenomegaly: Spleen not palpable;
 3. Complete response in constitutional symptoms: Absence of constitutional symptoms (fever, drenching night sweats, or $\geq 10\%$ weight loss);
 4. Complete response in platelet count: Platelet count $150-400 \times 10^9/L$;
 5. Complete response in leukocyte count: Leukocyte count $4-10 \times 10^9/L$.

Document: PPD

Author: PPD

Version Number:

V2.2

Version Date:

21 March 2018

Template No: CS_TP_BS016 – Revision 3

Reference: CS_WI_BS005

Effective Date: 01May2012

Copyright © 2012 Quintiles Transnational Corp. All rights reserved.

The contents of this document are confidential and proprietary to Quintiles Transnational Corp. Unauthorized use, disclosure or reproduction is strictly prohibited.

- **Major response:** Any response in both anaemia and splenomegaly without progression in constitutional symptoms **or** complete response in anaemia without progression in splenomegaly **or** partial response in anaemia in a baseline transfusion-dependent patient combined with response in constitutional symptoms without progression in splenomegaly **or** any response in splenomegaly combined with response in constitutional symptoms without progression in anaemia.
 1. Partial response in splenomegaly: Either $\geq 50\%$ decrease in spleen size if baseline ≤ 10 cm from left costal margin (LCM) or $\geq 30\%$ decrease if baseline > 10 cm from LCM.
 2. Partial response in platelet count: A $\geq 50\%$ decrease in platelet count if baseline $> 800 \times 10^9/L$ or platelet count increase by $\geq 50\% \times 10^9/L$ if baseline $< 100 \times 10^9/L$.
 3. Partial response in leukocyte count: A $\geq 50\%$ decrease in leukocyte count of baseline $> 20 \times 10^9/L$ or leukocyte count increase by $\geq 1 \times 10^9/L$ if baseline $< 4 \times 10^9/L$
 4. Progression in anaemia: A haemoglobin decrease of ≥ 2 g/dL **or** a 50% increase in transfusion requirement **or** becoming transfusion dependent
 5. Progression in splenomegaly: A $\geq 50\%$ increase in spleen size if baseline ≤ 10 cm from LCM **or** a $\geq 30\%$ increase if baseline > 10 cm from LCM.
 6. Progression in constitutional symptoms: Appearance of constitutional symptoms.

- **Moderate response:** Complete response in anaemia with progression in splenomegaly **or** partial response in anaemia without progression in splenomegaly **or** any response in splenomegaly without progression in anaemia and constitutional symptoms.

- **Minor response:** Any leukocyte- **or** platelet-based response without progression in anaemia, splenomegaly, **or** constitutional symptoms.

- **No response:** Any response that does not qualify at least as minor response.

In all cases (PV, ET and MF patients), the disease-related systemic symptoms are evaluated directly by patients according to MPN-SAF QOL questionnaire [8, 9].

In all cases, the response status of the patient can be reviewed by a panel of independent Investigators, if necessary.

In all cases, the medical judgment of the Investigator's is taken into account. In particular, if the Investigator's clinical response assessment – that takes into account the overall medical judgment of the specific patient's case - is not in agreement with the exact application of the clinico-haematological ELN or EUMNET response criteria , the Investigator's assessment will supersede the “mathematical”

Document PPD

Author: PPD

Version Number:

V2.2

Version Date:

21 March 2018

Template No: CS_TP_BS016 – Revision 3

Reference: CS_WI_BS005

Effective Date: 01May2012

Copyright © 2012 Quintiles Transnational Corp. All rights reserved.

The contents of this document are confidential and proprietary to Quintiles Transnational Corp. Unauthorized use, disclosure or reproduction is strictly prohibited.

application of these criteria and used for analysis into study report. Also mathematical application of ELN response criteria (not agreed by the medical site team) will be analyzed.

